7.4.2 Serious Adverse Event Reporting

The reporting of SAEs by the Sponsor or designee to the regulatory authorities is a regulatory requirement. Each regulatory authority has established a timetable for reporting SAEs based upon established criteria.

Serious AEs must be reported within 24 hours of discovery to the Sponsor or its designee; use the appropriate form for initial and/or follow-up reporting.

At a minimum, events identified by the Sponsor to require expedited reporting as serious, unexpected, and related to study drug must be brought to the attention of the responsible Institutional Review Board (IRB), as per applicable regulations. These will be provided by the Sponsor after their assessment. It is the Investigator’s responsibility to provide these expedited reports, and any new and significant information, to the responsible IRB.

When an SAE occurs, Investigators will review all documentation related to the event and will complete the paper SAE form (for initial and/or follow-up information) and fax or email (within 24 hours of discovery) to the contact information provided on the SAE form.

Subjects will be followed through the safety follow-up period for 30 days after last dose of study drug for any SAEs and/or other reportable information until such events have resolved or the Investigator, in conjunction with the Sponsor, deems them to be chronic or stable.

In the event of any SAE (other than death), the study subject will be instructed to contact the Investigator (or designee) using the telephone number provided in the informed consent form (ICF). All subjects experiencing an SAE will be seen by the Investigator or designee as soon as is feasible following the report of the SAE.

Serious AEs occurring greater than 30 days after last dose of study drug should be reported if in the judgment of the Investigator there is “a reasonable possibility” that the event may have been caused by the product.

SAEs should also be reported to the institutional review board/ethics committee (IRB/EC) according to local regulations.

7.4.3 Reporting of Pregnancy

Any female subject who becomes pregnant during the study (with or without AEs) must be withdrawn from the study and the pregnancy must be reported on the Pregnancy form within 24 hours of discovery to the Sponsor or its designee. Any female subject who becomes pregnant during the study will be followed through the pregnancy outcome.

Any AEs that are the consequence of pregnancy and which meet the criteria for serious should also be reported via the SAE form.

7.4.3.1 Reporting Paternal Drug Exposure

Paternal drug exposure is defined as a father’s exposure to a medicinal product before or during his partner’s pregnancy. Any paternal drug exposure cases must be reported to the Sponsor within 24 hours of discovery via the Pregnancy form. Any AEs that are the consequence of paternal drug exposure and which meet the criteria for serious must also be reported to the Sponsor within 24 hours of discovery via the SAE form.

7.4.4 Reporting of Overdose

An overdose is a deliberate or inadvertent administration of a treatment at a dose higher than the maximum recommended dose per protocol. It must be reported to the Sponsor or designee on the Overdose form within 24 hours of discovery. In addition, all events of overdose are to be captured as protocol deviations.

8 CLINICAL MONITORING

Routine monitoring of study sites is described in [Section 11](#).

Clinical site monitoring is conducted to ensure that the rights and well-being of human subjects are protected, that the reported study data are accurate, complete, and verifiable, and that the conduct of the study is in compliance with the currently approved protocol and amendment(s) as applicable, with GCP, and with applicable regulatory requirements. Details of the study site monitoring process are described in a separate clinical monitoring plan document.

9 STATISTICAL METHODS AND DATA ANALYSIS

9.1 Statistical and Analytical Plans

Statistical methods will be documented in detail in a statistical analysis plan (SAP) to be approved by the Sponsor prior to database lock.

9.2 Statistical Hypotheses

No formal testing of efficacy or safety hypotheses is planned. Efficacy and safety outcomes will be summarized descriptively.

9.3 Sample Size Determination

This is an exploratory study and is not powered for statistical significance. Formal sample size calculations were not used to determine sample size.

9.4 Subject Populations for Analysis

The **Safety Analysis Set** will consist of all subjects who have taken at least 1 dose of study drug. The Safety Analysis Set will be used for all safety analyses.

The **Full Analysis Set** will consist of all randomized subjects who have taken at least 1 dose of study drug and have both a Baseline value and at least 1 post-Baseline value for the mFSQ total score. The Full Analysis Set will be used for all efficacy analyses.

9.5 Statistical Analyses

All safety and efficacy measures will be summarized using descriptive statistics.

For continuous variables, the following summary statistics will be provided: number of subjects, mean, standard error of the mean, standard deviation, minimum, maximum, and median. For categorical variables, summaries will include the number and percentage of subjects in each category, using the number of subjects with non-missing values as the denominator for the percentages (unless otherwise specified).

All efficacy analyses will be based on the Full Analysis Set. All confidence intervals will be 2-sided 95% CIs, unless stated otherwise.

Baseline is defined to be the last non-missing value prior to the first dose of study drug.

9.5.1 Primary Analyses

The primary efficacy endpoint, change from baseline to Week 16 in the mFSQ total score, will be evaluated using a mixed-effects model for repeated measures (MMRM). The response variable is the change from Baseline to Weeks 4, 8, 12, and 16 and the fixed effects include visit (Weeks 4, 8, 12, and 16), corresponding Baseline score, and the Baseline score-by-visit interaction. The mFSQ total score will be calculated as the unweighted mean of the subscale scores (Basic ADL, Intermediate ADL, Psychological Function, Social Activity and Quality of Social Interaction). The Work Performance subscale will be excluded, given the age and non-employment status of the intended patient population.

Summary statistics for the mFSQ total score (observed and change from Baseline), least-squares (LS) means and the corresponding 95% CI will be presented.

9.5.2 Secondary Analyses

The change from Baseline to Week 16 in the secondary endpoints measured at scheduled visits, including Schwab & England ADL Scale (Patient and Caregiver), MDS-UPDRS Part I (Patient and Caregiver), and MDS-UPDRS Part II (Patient and Caregiver) will be summarized using an MMRM model similar to that described for the primary analysis, except that the Baseline value of the endpoint being analyzed will be included in the model instead of the Baseline mFSQ total score.

For CGI-I the response variable is the observed score at Week 16 and the MMRM will include fixed effects for visit (Week 2, 4, 8, 12, and 16), Baseline CGI-S score, and Baseline CGI-S score-by-visit interaction.

For PGI-I the response variable is the observed score at Week 16 and the MMRM model will include a fixed effect for visit (Week 2, 4, 8, 12, and 16).

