	
Secondary Analyses
 
Each of the secondary endpoints will be analyzed using the MMRM model similar to that described for the primary analysis. For CGI-I the baseline CGI-S score will be used as the covariate in the MMRM model.
 
Safety Analyses
 
Adverse events will be classified into standard terminology using the Medical Dictionary for Regulatory Activities (MedDRA). All adverse events (AEs) will be listed and TEAEs will be summarized by system organ class and preferred term.
 
A TEAE is defined as an AE that occurs after the first dose of study drug and up to 30 days after the last dose of study drug. Summaries by maximum severity and by relationship to study drug as assessed by the investigator will also be provided. Serious TEAEs, fatal AEs, and TEAEs leading to discontinuation will also be summarized.
 
The serum clinical chemistry, hematology, and urinalysis results at each time point will be summarized. Change from Baseline values will also be summarized.
 
The number and percentage of subjects with PCI post-Baseline values will be summarized at each post-Baseline visit and overall post-Baseline for selected parameters. The PCI criteria will be specified in the statistical analysis plan.
 
Vital signs, body weight, and BMI at Baseline and each post-Baseline visit will be summarized. Change from Baseline values will also be summarized.
 
The results of the physical examinations at each visit will be tabulated.
 
Electrocardiogram parameters at study visits will be summarized. Change from Baseline values will also be summarized. Categorical analyses will be conducted on the incidence of subjects with prolonged QTc intervals and changes in QTc intervals in accordance with ICH guidelines.
 
For the C-SSRS, the number and percentage of subjects with suicidal ideation or suicidal behavior during the study will be tabulated.

Date	20 May 2021

Figure S-1 Schematic of Study Design for ACP-103-063

Abbreviations: EOT: end of trial; ET: early termination; QD: once daily

Table S-1 Schedule of Events and Assessments for ACP-103-063

Period	Screening	Treatment						Safety Follow-up	
		Baseline	0	2	4	8	12		
Visit Week	-5 to 0	1	2	3	4	5	6	7/ET ^b	8
Visit Number	1			±3	±3	±3	±3	±3	+4
Visit window (days)									
Type of Visit	clinic	clinic	clinic	clinic	clinic	clinic	clinic	clinic	telephone
Informed consent of subject	X								
Informed consent of caregiver or study partner	X								

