Inclusion/exclusion criteria	X	X							
Medical history and demographics	X								
Weight, height, BMI	X	X						X	
Physical examination	X							X	
12-lead ECG ^c	X	X			X			X	
Vital signs ^d	X	X	X	X	X	X	X	X	
Clinical laboratory tests	X	X		X				X	
Urine drug screen	X								
Pregnancy test ^e	X	X		X	X	X	X		
MMSE	X								
C-SSRS	X	X	X	X	X	X	X		
FSQ	X	X		X	X	X	X		
Schwab & England ADL Scale (Patient)	X	X	X	X	X	X	X		
Schwab & England ADL Scale (Caregiver)	X	X	X	X	X	X	X		
NPI domains A and B	X	X							
NPI-Q Nighttime Behavior Domain only		X	X	X	X	X	X	X	
MDS-UPDRS Parts I and II (Patient)	X	X	X	X	X	X	X	X	
MDS-UPDRS Parts I and II (Caregiver)	X	X	X	X	X	X	X	X	

Table S-1 Schedule of Events and Assessments for ACP-103-063 (Continued)

Period	Screening	Treatment						Safety Follow-up
		Baseline						
Visit Week	-5 to 0	0	2	4	8	12	16/EOT	20 ^a
Visit Number	1	2	3	4	5	6	7/ET ^b	8
Visit window (days)			±3	±3	±3	±3	±3	+4
Type of Visit	clinic	clinic	clinic	clinic	clinic	clinic	clinic	telephone
CGI-S specific to H&D	X	X	X	X	X	X	X	
CGI-I specific to H&D			X	X	X	X	X	
PGI-I specific to H&D			X	X	X	X	X	
VRFCAT	X	X		X			X	
Caregiver Strain Index	X	X	X	X	X	X	X	
Geriatric Depression Scale (Short Form)	X	X	X	X	X	X	X	
Concomitant medication	X	X	X	X	X	X	X	X
Assessment of adverse events		X	X	X	X	X	X	X
Dispense study drug		X	X	X	X	X		
Study drug return			X	X	X	X	X	
Study drug accountability			X	X	X	X	X	

Abbreviations: ADL=activities of daily living; BMI=body mass index; CGI-I=clinical global impression – improvement; CGI-S=clinical global impression – severity; C-SSRS=Columbia-Suicide Severity Rating Scale; ECG=electrocardiogram; EOT=end of trial; ET=early termination; FSQ= functional status questionnaire; H&D=hallucinations and delusions; MMSE=mini-mental state examination; NPI=neuropsychiatric inventory; NPI-Q=neuropsychiatric inventory – questionnaire; PGI-I=patient global impression – improvement; MDS-UPDRS=Movement Disorders Society – Unified Parkinson’s Disease Rating Scale; VRFCAT=virtual reality functional capacity assessment tool

^a The safety follow-up telephone call visit is to occur 30 (+4) days after the last dose of study drug, nominally at Week 20 for completers and earlier for ET subjects.

^b A subject terminating early should at a minimum complete assessments of safety (vital signs, ECG, AEs, clinical laboratories, C-SSRS) and, if possible, complete all Week 16 assessments.

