## 12.4 Handling of Missing Data

Scores that are missing, after any imputation of individual missing items as described in Section 5.2, will not be imputed. MMRM analyses will be used as the statistical approach for handling of missing data. Model parameters are simultaneously estimated using restricted maximum likelihood estimation. The MMRM method is unbiased in the estimation of treatment effect under the missing at random assumption and can be thought of as attempting to estimate the treatment effect that could have been observed if all subjects had continued on study for the full study duration.

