## 12.8 Mixed Model Repeated Measures (MMRM)

The MMRM method with restricted maximum likelihood estimation (REML) will be used for selected efficacy endpoints. The dependent variable will be the change from Baseline. The independent variables in the model will include effects for visit, Baseline score, and Baseline score-by-visit-interaction. An unstructured covariance matrix will be used to model the within patient errors, and the Kenward-Roger approximation will be used to adjust the denominator degrees of freedom.

In the event that the model fails to converge using the unstructured covariance matrix, then only descriptive statistics will be presented.

Summary statistics (observed and change from Baseline, LS means with corresponding two-sided 95% confidence intervals (CIs), and p-values will be presented at each post-Baseline visit for the Full Analysis Set. The primary comparison is based on the LS mean change from Baseline to Week 16.

LS mean  $\pm$  SE from the MMRM model over time for the change from Baseline values will be displayed in line plots for the Full Analysis Set.

The above MMRM model will be used for each of the primary, secondary, and exploratory endpoints. CGI-I score will be analyzed using a similar MMRM model with effects for visit, Baseline CGI-S score, and Baseline CGI-S score-by-visit interaction. PGI-I score will be analyzed using an MMRM model with an effect for visit.

NPI-Q Caregiver and Distress scores will be summarized in shift tables to determine the number and percentage of subjects with Severity scores classified as none, mild, moderate, or severe relative to the same classification at the Baseline visit; and the number and percentage of subjects with Distress scores classified as not distressing at all, minimal, mild, moderate, severe, and extreme or very severe relative to the same classification at the Baseline visit. For the by-visit shift summary, the denominator is the number of subjects with non-missing values at Baseline and the given visit for the given parameter.

For each of the continuous efficacy endpoints (except for CGI-I and PGI-I) the null hypothesis is that the change from baseline to a certain time-point is equal to 0. The corresponding alternative hypothesis is that the change from baseline to a certain endpoint is not equal to 0.

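### PGI-I is modelled on visit alone while CGI-I is adjusted for Baseline CGI-S; adding that covariate would guard the Week 16 PGI-I mean against a small, conditional dropout bias

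*Protocol*

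**What the plan says.** For PGI-I, Protocol 9.5.2 states that "the MMRM model will include a fixed effect for visit (Week 2, 4, 8, 12, and 16". SAP 12.8 agrees: "PGI-I score will be analyzed using an MMRM model with an effect for visit". For CGI-I the same two sections add "Baseline CGI-S score, and Baseline CGI-S score-by-visit interaction" to the visit effect.

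Both scales are 7-point ratings of change since Baseline in hallucinations and delusions, one by the clinician and one by the patient (SAP 5.2.8 and 5.2.9). Neither has a Baseline value of its own. Baseline CGI-S is available: the row "CGI-S specific to H&D" in Table S-1 is marked at Screening, Baseline and every treatment visit, and a score of at least 4 at Visit 2 is required for entry (inclusion criterion 10).

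The protocol synopsis says of the secondary endpoints: "Each of the secondary endpoints will be analyzed using the MMRM model similar to that described for the primary analysis". It then names a substitute covariate for CGI-I only.

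On missing data, SAP 12.4 says: "The MMRM method is unbiased in the estimation of treatment effect under the missing at random assumption". SAP 12.8 adds: "An unstructured covariance matrix will be used to model the within patient errors".

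**The concern.** PGI-I is the only secondary endpoint whose model has no baseline term, and neither document says why. Missing at random is always relative to what the model contains. For PGI-I it contains only visit and the subject's own earlier PGI-I scores. If baseline psychosis severity influences who leaves, and also carries information about Week 16 PGI-I that the earlier scores do not, the assumption in SAP 12.4 fails for this endpoint although a measured variable could repair it.

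A route is imaginable from the plan's own rules. Protocol 4.4 lists lack of efficacy and prohibited medication as reasons for discontinuation, and Appendix A prohibits all other antipsychotics. Whether more severe subjects leave more often by these routes is not shown anywhere.

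At stake is the only patient-rated endpoint devoted to psychosis, which SAP 12.8 reports with a confidence interval and a nominal test against 4 (no change).

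**Working it through.** **The plan's own figures.** Enrolled: 89 × (1 − 0.40) = 53.4, stated as 53. Completers: 53 × (1 − 0.20) = 42.4, stated as 42. Both reproduce. The plan gives no SD, no dropout by severity and no expected effect for PGI-I, so the rest is assumption.

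**When the visit-only model is unbiased.** With an unstructured covariance, the model in effect predicts a leaver's later scores from that subject's earlier PGI-I. The Week 16 mean is biased by omitting CGI-S only if, among subjects with the same PGI-I history, leavers and stayers differ in Week 16 PGI-I because they differ in Baseline CGI-S. That needs two links: CGI-S to dropout, and CGI-S to Week 16 PGI-I given the earlier scores.

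**Assumed inputs.** PGI-I SD 1.2; Baseline CGI-S of 4/5/6/7 in 55/33/10/2% (mean 4.59, SD 0.75); dropout odds ratio 2 or 3 per CGI-S point; last observed visit spread over Weeks 2 to 12; lag-1 correlation of PGI-I 0.6 (0.8 in the mediated case). No PGI-I at early termination is simulated.

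**Bias of the raw completer mean, by hand.** With odds ratio 3 and 20% overall dropout, the dropout probabilities at CGI-S 4/5/6/7 are 0.10/0.25/0.50/0.75. Shares retained: 0.55 × 0.90 = 0.495; 0.33 × 0.75 = 0.2475; 0.10 × 0.50 = 0.05; 0.02 × 0.25 = 0.005; total 0.7975. Mean CGI-S of completers = (4 × 0.495 + 5 × 0.2475 + 6 × 0.05 + 7 × 0.005) / 0.7975 = 3.5525 / 0.7975 = 4.455, which is 0.135 below 4.59. A correlation of 0.3 means a slope of 0.3 × 1.2 / 0.75 = 0.48 PGI-I points per CGI-S point, so the completer mean is off by −0.135 × 0.48 = −0.065. At correlation 0.5 the slope is 0.80 and the error −0.108. Simulation gives the same values.

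**What the MMRM leaves.** Large-sample simulation (600,000 subjects), maximum likelihood under monotone dropout that depends only on Baseline CGI-S. Bias of the Week 16 mean in points; a negative value looks better than the truth:

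| Link from CGI-S to PGI-I | OR 2, 20% dropout | OR 3, 20% | OR 3, 35% (stress case) |
|---|---|---|---|
| None | 0.00 | 0.00 | 0.00 |
| Only through earlier observed PGI-I | 0.00 | 0.00 | 0.00 |
| Constant, r = 0.3, equal correlations between visits | −0.01 | −0.01 | −0.02 |
| Constant, r = 0.3, correlation decaying with time | −0.02 | −0.04 | −0.06 |
| Growing to r = 0.3 at Week 16 | −0.03 | −0.05 | −0.08 |
| Growing to r = 0.5 at Week 16 | −0.05 | −0.09 | −0.13 |

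With Baseline CGI-S and its visit interaction added, evaluated at the mean CGI-S of all simulated subjects, the bias is at most 0.002 in every row.

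**Direction.** A second simulation used SD 1.1, within-subject correlation 0.5, 22 to 26% dropout depending on CGI-S (log-odds 0.5 or 1.0 per point) and on the previous PGI-I. A slope of −0.5 points per CGI-S point gave +0.023 and +0.049; +0.5 gave −0.027 and −0.057; +0.8 gave −0.041 and −0.091. Adjusting for CGI-S left 0.001 or less. A further run at 20% dropout gave about 0.03 to 0.10 in either direction when CGI-S predicted Week 16 PGI-I beyond the earlier scores.

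**Scale.** The standard error with 42 subjects is 1.1/√42 = 0.17 to 1.2/√42 = 0.19. For SD 1.2 the 95% half-width is 1.96 × 0.185 = 0.36. A bias of 0.085 is 0.085/0.185 = 0.46 of a standard error; 0.10 is 0.54. At half a standard error, the coverage of a nominal 95% interval is Φ(1.46) − Φ(−2.46) = 0.928 − 0.007, about 92%.

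**The case against.** The strongest reply is that the two documents make the same explicit choice. CGI-I and CGI-S are paired clinician ratings; PGI-I is the patient's own and has no baseline partner, so borrowing the clinician's severity score is an option and not an obligation. That stands: there is no contradiction to repair. A reader might infer one from the synopsis, but it asks only for a similar model and does not promise PGI-I a covariate.

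The second reply is that the plan already absorbs part of the problem. Withdrawal for poor response would tend to follow poor PGI-I scores at Weeks 2 to 12, which the unstructured covariance uses. Subjects terminating early are asked to complete the Week 16 assessments if possible (Table S-1, footnote b), and SAP 5.3.1 admits early-termination visits to the analysis windows. This also stands. It reduces the likely bias but does not remove any residual link with severity.

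The third is that this is a secondary endpoint in an unpowered, exploratory, single-arm study without multiplicity control, and nothing shows that a shift of this size would change a conclusion. That limits the importance of the point. It is not a reason to leave out a covariate already collected and already used for CGI-I.

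**Conclusion.** The point holds as a minor, conditional improvement. The Week 16 PGI-I mean could be biased if Baseline CGI-S predicts dropout and also predicts later PGI-I beyond the earlier observed scores. At the planned 20% dropout, the size is about 0.01 to 0.10 points on a 7-point scale, roughly half a standard error or less. That range rests wholly on assumed SDs, correlations, severity mix and dropout odds.

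Three stronger readings are tempting and not supported:

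- A reader might infer that severity-dependent dropout is enough to bias the mean. It is not: the first two rows of the table have such dropout and no bias.
- A reader might infer that the visit-only mean flatters the drug. The sign follows the association between CGI-S and PGI-I, which the documents do not give.
- A reader might infer that CGI-I and PGI-I cannot be compared. No such comparison is planned, and in a single-arm linear model with complete data the adjusted mean at the average Baseline CGI-S equals the visit-only mean.

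**What to change.** In Protocol 9.5.2 and SAP 12.8, give PGI-I the CGI-I model: fixed effects for visit, Baseline CGI-S and Baseline CGI-S by visit. State that LS means are evaluated at the mean Baseline CGI-S of the Full Analysis Set with each subject counted once. Averaging over visit records would weight that mean towards subjects who stay and bring back part of the bias. Keep the visit-only model as a sensitivity analysis.

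The cost is one sentence, with no new data and no extra covariance parameters. The small downsides are five more fixed-effect parameters and a standard error conditional on the observed baseline, as in the plan's other MMRMs with a baseline covariate. The change does not reach subjects with no post-baseline mFSQ total score: they are outside the Full Analysis Set (SAP 4.2), so their severity never enters the mean.
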